1.3. Research questions and hypotheses, theoretical approach and methodology

RESEARCH QUESTION: Through a decentralized RCT investigating two digital interventions with differentiated levels of therapist-support, the goal is to expand knowledge about transdiagnostic relapse prevention strategies that can easily be scaled up and have the potential of cost-effectively reducing relapse rates for adolescents in an important phase of life. Alongside, collecting empirical

[figure not shown]
evidence for the association between repetitive negative thinking and relapse will increase knowledge regarding underlying mechanisms of relapse prevention strategies.

DESIGN: The trial is designed as a three-armed randomized single-blind open-label clinical trial (1:1:1) with stratification based on gender. It will not be possible to blind participants in the study due to the obvious differences between the interventions. We will investigate the effects of the “Tankevirus”-therapist-guided intervention and the “Tankevirus” smartphone app, respectively, and compare the effect of these transdiagnostic interventions to assessment only. All arms will be conducted in combination with care as usual. Assessments are done digitally, with no influence from the researcher. The primary endpoint of the trial will be analyzed blinded to treatment allocation. The trial will be preregistered with clinicaltrials.gov.

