INTERVENTIONS: “Tankevirus” is an award-winning psychological intervention developed for adolescents aged 16 and above, including a book, a mastery course, and a smartphone app. It is based on the principles of CBT to help individuals identify and challenge negative thought patterns that can lead to anxiety and depression. “Tankevirus” has been extensively evaluated. From 2017-2021, 50.000 students took part in the overarching “Tankevirus” School program, and 9 out of 10 thought the interventions were useful and would recommend it to a fellow student. The “Tankevirus” smartphone app is freely available, and within 16 months, it was downloaded by 26.000 adolescents. Based on patient reported outcome measures, 7 out of 10 reported improvements in overall health and increased quality of life. The app includes several components to increase engagement with the intervention material, which is a necessary prerequisite for digital mental health interventions to be effective (26), and smartphone apps which have elements built in to promote engagement are associated with larger effect sizes (29). In this project we will include two different formats of the “Tankevirus”-interventions, in addition to a control condition:

- **“Tankevirus” therapist-guided group intervention:** The intervention will be delivered by therapists having extensive experience with this age group in the form of 3 weekly 75-minutes sessions to groups of approximately 30-35 participants. An online GDPR-compliant webinar-platform including chat-options will be used (edumeet.org). Adolescents will remain anonymous to each other to decrease barriers to participation. The adolescents will book their preferred timeslot online. For the participants randomized to this intervention, a certain waiting period (~1 week) must be expected. We will keep record of number of days waiting for each person and include this as covariate in the analysis.
- **“Tankevirus” smartphone app:** The app will be downloaded to their personal smartphone, and the app will give push-notifications once new modules are released – every day for 3 weeks. The app has several procedures built in for engagement purposes but will not involve contact with a therapist. Usage data will be recorded to verify compliance. The app is developed in accordance with the requirements of the Norwegian Health Authorities and complies with data protection laws.

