- **Assessment-only:** All assessments will be conducted, but no intervention will be provided to this group. The assessment only condition is necessary for investigating natural trajectory and form the baseline level for assessing risk reduction in the interventional groups.

Figure 1. Screenshot from GooglePlay of the “Tankevirus” smartphone app.

All interventions and assessments for all trial arms will be fully digitalized through a research app, which is essentially a modification to the already developed “Tankevirus”-app, including all preassessments and follow-ups. Human interaction is limited to the therapist-led group, otherwise automated nudges and notifications will remind the adolescents to complete assessments. This will be beneficial when considering the scalability and implementation of the intervention, should it be successful, and for evaluating whether human interaction indeed is a driver of the effect between interventions.

HYPOTHESIS: The main hypothesis is that the outcome related to the therapist-guided group intervention will be more effective in reducing number of relapses and time to relapse during the follow-up period when compared to the app-based approach, and that the app-based approach will be more efficacious compared to an assessment-only condition/care-as-usual (the control group).

PARTICIPANTS: Participants will primarily be recruited through large scale marketing campaign in social media (i.e., TikTok, Snapchat, Instagram) and web pages of user organizations, informing about this trial and the opportunity to take part. This is the most efficient way of reaching eligible participants, as clinicians seldom refer to such a trial ([name], PI of the StayFine-trial targeting adolescents in remission, *personal communication*, 21.07.24). Overall, 90 % of Norwegian adolescents are on social media (30). Currently, we have established contact with the social media coordinator in Mental Helse Ungdom. We will also post physical adds at places we expect adolescents to see them. Through other ongoing projects we have contact with ~150 general practitioners and we have established a collaboration with the low-threshold service UngArena.

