The combination of elaborate marketing campaigns in social media and the research app will allow for a very efficient recruitment, eligibility check and data collection. Those being interested will register online after confirming inclusion criteria: 1) between the ages of 16-19, 2) have previously sought professional help for anxiety and/or depressive symptoms, 3) have been feeling fine or mostly fine for the last two months. Before further assessment and trial inclusion, the adolescent will sign informed consent digitally. After consent is obtained, they will be invited to download the research app. To ensure eligibility, preassessment with the digitalized self-report format of the clinical interview Composite International Diagnostic Interview 5th revision (CIDI 5.0 (31)) will be conducted to make sure that the adolescent have had a previous episode of depression and/or an anxiety fulfilling the DSM-5 criteria, and no current ongoing episode or ongoing anxiety disorder before trial entry and randomization are conducted.

Table 1. Participant eligibility

Inclusion criteria

 • Currently in full or partial remission for a minimum of 2 months from a depressive disorder or an anxiety disorder. • Age between 16-19. • Native or fluent Norwegian or Scandinavian language skills. • Willingness to take part even when allocated to the non-preferred intervention.
Exclusion criteria

 • Ongoing depressive disorder, ongoing anxiety disorder. • Recent (within ~1 year) completion of the “Tankevirus”-intervention. • No available smartphone.

PRIMARY ENDPOINT: The primary endpoint will be time until relapse and number of relapses to depression during the 12-months follow-up post-randomization. To assess relapse, the app will give notifications for biweekly assessments with the ultra-brief PHQ-4 (32) assessing both anxiety and depressive symptoms. If the depression subscale indicates relapse (score ≥ 3), the remaining questions from PHQ-A (33), that is the adolescent version of PHQ-9 (34), will pop-up. The items in PHQ-9 aligns with the diagnostic criteria for major depressive disorder as described in the Diagnostic and

Statistical Manual of Mental Disorders (35) and an algorithm can therefore indicate depressive relapse (36). This procedure of biweekly assessments will also provide a precise measure of time to relapse.

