STATISTICAL POWER: For the primary endpoint investigating number of relapses within the follow-up period, we will conduct a fixed effects omnibus ANOVA. Presuming Cohen's $f = .25$, alpha = .0167 (.05/3; Bonferroni corrected) and power = .8 including three groups, we will require a total sample size of 207 (GPower 3.1). Presuming 15 % dropout, we will need 238 adolescents to take part in the study. For time to relapse, the power analysis was performed using Monte Carlo simulation. A large pool of simulated survival data was generated, reflecting a hazard ratio of 0.6 between two groups, a 15% annual dropout rate with competing risk, and a 1-year observation period. The simulation titrated the sample size, drawing 10.000 random samples at each step and fitting Cox proportional hazards models. Power was estimated as the proportion of samples yielding statistically significant results at the 0.05 level. The analysis concluded that approximately 165 individuals per group, meaning that a total of 495 adolescents would be required to achieve 80% power for detecting a hazard ratio of 0.6 under the specified conditions. This simulation method accounts for the complexities of survival data, including censoring and limited observation time, providing a robust sample size estimate for the study design. All randomized participants will be subjected to analysis in accordance with an intention to-treat approach. The multiarmed parallel group randomized trial will be reported according to the extensions recommended by CONSORT (44).

RISK: Recruitment is the main risk factors of this trial. A few trials are currently under way in adolescent populations (e.g., StayFine trial (16), RuMeChange (15)) and in the first, they were in contact with 3018 adolescent during a three-year period. Their strict inclusion criteria and elaborate pre-inclusion assessments hindered several from participating, but still they had 589 eligible

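### Days waiting arises after randomisation and is described only for the therapist-guided arm, yet it is to be a covariate in the analysis without restriction to that arm

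*Protocol*

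**What the plan says.** All passages are in Protocol section 1.3.

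- **INTERVENTIONS, therapist-guided group.** Participants choose their own session: "The adolescents will book their preferred timeslot online". Then: "For the participants randomized to this intervention, a certain waiting period (~1 week) must be expected". Then the rule at issue: "We will keep record of number of days waiting for each person and include this as covariate in the analysis". It does not say which analysis is meant, whether it covers that arm only, or what value the other arms take.
- **INTERVENTIONS, other arms.** For the app, "the app will give push-notifications once new modules are released – every day for 3 weeks"; no wait is described. Assessment-only receives no intervention, so a wait has no meaning there.
- **PRIMARY ENDPOINT.** The outcome is "time until relapse and number of relapses to depression during the 12-months follow-up post-randomization", so the wait lies within follow-up.
- **HYPOTHESIS.** One of the two main comparisons is that "the therapist-guided group intervention will be more effective in reducing number of relapses and time to relapse during the follow-up period", against the app.
- **DESIGN.** "The primary endpoint of the trial will be analyzed blinded to treatment allocation".
- **STATISTICAL POWER.** The time-to-relapse simulation is described as "reflecting a hazard ratio of 0.6 between two groups, a 15% annual dropout rate with competing risk, and a 1-year observation period", fitted with Cox models. It names no waiting-time covariate. All randomised participants are to be analysed by intention to treat.

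**The concern.** A covariate in a randomised comparison should be fixed before allocation. This one is a consequence of allocation to one arm, and partly of the participant's own choice afterwards.

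If it enters a model that compares arms, the consequences depend on its coding elsewhere:

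- **Coded 0 in the other arms.** The therapist-arm coefficient is then the effect at zero wait. That is not the effect of being allocated to the therapist-guided programme, for which the protocol itself expects a wait of about a week. Because the variable is strongly collinear with the arm indicator, the standard error grows. If those who book late differ in prognosis from those who book early, the estimate is also biased, in a direction the protocol gives no means of predicting.
- **Coded missing in the other arms.** A complete-case model loses both comparators and the contrast cannot be fitted.

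Under either coding the variable shows the analyst who is in the therapist-guided arm, which sits badly with a blinded primary analysis. A participant in that arm who never books has no defined wait, although intention to treat keeps that participant in the analysis.

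At stake are the contrasts with the therapist-guided arm, including the comparison with the app in the main hypothesis.

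**Working it through.** **Inputs from the protocol:** hazard ratio 0.6, 165 per group, 15% annual dropout, 1-year observation, alpha 0.05 (taken as two-sided), mean wait about 1 week (7 days).

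**Assumed, not in the protocol:** the SD of the wait (2 to 14 days shown), wait coded 0 outside the therapist-guided arm, exponential relapse times, and the control relapse risk, which was solved for in step 1.

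**1. The plan's own figures.** The noncentral F calculation for f = 0.25, alpha 0.0167 and three groups gives N = 207 (power 0.805), as stated. For time to relapse, the events needed are 4(1.96 + 0.8416)² / (ln 0.6)² = 31.40 / 0.2609 = 120.3. With control hazard 0.632 per year (12-month risk 1 − e^−0.632 = 46.8%) and dropout hazard −ln 0.85 = 0.1625, the expected events among 165 are:

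- control: 165 × (0.632/0.7945)(1 − e^−0.7945) = 72.0
- therapist-guided: 165 × (0.3792/0.5417)(1 − e^−0.5417) = 48.3

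The total is 120.3, so 165 per group reproduces at about 80% power if the control risk is about 47%.

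**2. Precision, relapse-count ANOVA.** With wait mean m and SD s in one arm and 0 elsewhere, the variance of a contrast with that arm is multiplied by 1 + m²/(2s²). At s = 3.5 this is 1 + 49/24.5 = 3.0, so the SE is multiplied by 1.73.

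**3. Precision, Cox model.** The approximate variance is 1/48.3 + 1/72.0 + (m²/s²)/48.3. Without the covariate, the square root of 0.0346 is 0.186. At s = 3.5, the square root of 0.0346 + 4/48.3 is 0.343. Simulation (10,000 replicates per SD, gamma-distributed wait unrelated to relapse; SE at SD 14 from 2,500 replicates) gave 0.187 and 79% power without the covariate. With it:

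| SD of wait (days) | ANOVA SE multiplier | Cox SE of log HR | Power at HR 0.6 |
|---|---|---|---|
| 2 | 2.67 | 0.542 | 14% |
| 3.5 | 1.73 | 0.347 | 31% |
| 5 | 1.41 | 0.277 | 44% |
| 7 | 1.22 | 0.238 | 57% |
| 10 | 1.12 | 0.214 | 66% |
| 14 | 1.06 | 0.201 | 72% |

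A separate simulation with control hazard 0.655 gave 15%, 32% and 45% at SD 2, 3.5 and 5, from 80%.

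**4. Three-arm Cox model**, HR 0.6 assumed at each step. Therapist-guided versus app falls from 60% to 20%, 38% and 52% at SD 3.5, 7 and 14. App versus assessment-only stays at 79% (SE 0.187 with and without the covariate).

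**5. Changed estimand.** If each day of waiting raises the hazard by 5% and the effect at the mean wait is 0.6, the adjusted coefficient targets 0.6 × 1.05^−7 = 0.43. Simulation gave 0.43, against 0.60 unadjusted.

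**6. Bias with no treatment effect.** Let prognosis carry log HR b per SD of wait. The adjusted log HR is then about −b × m/s. At s = 3.5 and b = 0.1 this is −0.2, or HR 0.82. Simulation (10,000 replicates) gave:

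| b per SD | SD 3.5: HR (type I error) | SD 3.5, sign reversed | SD 7: HR (type I error) | SD 7, sign reversed |
|---|---|---|---|---|
| 0.05 | 0.90 (6%) | 1.11 (7%) | 0.96 (6%) | 1.06 (6%) |
| 0.1 | 0.81 (9%) | 1.23 (12%) | 0.92 (7%) | 1.11 (8%) |
| 0.2 | 0.66 (27%) | 1.51 (32%) | 0.84 (13%) | 1.22 (17%) |
| 0.3 | 0.54 (51%) | 1.83 (58%) | 0.77 (25%) | 1.35 (31%) |

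Unadjusted, the HR is 1.00 and the type I error about 5% throughout.

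**7. Centred coding.** If the wait is centred within the therapist-guided arm, power stays at 79–80%. In the null scenarios at SD 3.5 with b = 0.05, 0.1 and 0.3, the HR is 1.00, 1.00 and 0.98, with rejection 5% each time. The harm therefore comes from zero coding and not from recording the wait.

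**The case against.** The strongest reply is that the protocol never says the wait is coded 0 elsewhere, nor that it enters a between-arm model. The sentence follows directly on one about participants randomised to the therapist-guided group, so a within-arm reading is natural, and on that reading nothing is wrong. Centring within the arm removes both the power loss and the bias. Coding and model choice are matters a protocol commonly leaves to the analysis plan, which is not shown.

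The sizes are also illustrative. The largest type I errors need the hazard to change by about 35% (e^0.3 = 1.35) per 3.5 days of booking delay, and nothing in the protocol says booking delay is related to prognosis. Without such a link, the extrapolation covers about 7 of 365 days, less than one biweekly assessment interval. Planning simulations often omit covariates, so the silence of the power section is not a defect in itself.

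Much of this stands. The figures are conditional on zero coding and the assumed SD, and the power-section point is only supporting. But the sentence is not an omission: it commits to the covariate, refers to the analysis without limit, and so permits the harmful reading as readily as the harmless one. An analysis plan that avoids the problem would have to narrow the protocol's wording. Centred adjustment is harmless in these checks, but keeping the wait out loses nothing against it and leaves no coding choice open.

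**Conclusion.** The concern holds and should be fixed. The protocol commits to a covariate that arises after allocation, is partly self-selected, and is described for one arm only, without confining it to that arm.

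Used in a between-arm model with zero coding, it changes what the therapist-guided contrasts estimate, inflates their standard error at any finite SD of wait, and biases them in either direction if booking delay is related to prognosis. The exact sizes rest on the assumed SD, control risk and prognostic link. The change of estimand and the loss of precision rest only on the zero coding. App versus assessment-only is not affected.

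**What to change.** Replace the sentence in the therapist-guided bullet with:

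> Number of days waiting will be recorded and reported descriptively, and may be examined as a predictor within the therapist-guided arm. It will not enter any between-arm model. Arms are compared as allocated, from randomisation, so that the wait is part of the therapist-guided strategy.

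The cost is one sentence of protocol wording. There is no change to data collection, sample size or participant burden.

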1.1. State of the art, knowledge needs and project objectives

Globally, it is estimated that 4.6 % of all adolescents in the age group 15-19 years, experience an anxiety disorder and 2.8 % experience depression (1). Together with behavioural disorders, these disorders are the number one cause of illness and disability in this age group. Single episodes of depression and anxiety during teenage years can be immediately serious and potentially life-threatening (2). It is also a risk factor for developing more severe affective disorders, long-term psychosocial, educational, and vocational impairments, poorer physical health, increased risk of suicide and self-harm, and dependence of illicit drugs (3-6). Anxiety in the adolescent years, is associated with three-fold increase of depression in early-adulthood (7). Often, the two disorders co-occur or cross over to one another, suggesting that transdiagnostic factors are of importance.

Treatment for adolescent anxiety and depression are moderately effective (8, 9) and use of mental health services attenuate negative long-term outcome (6). Still, many are left with residual symptoms after treatment, (10) and a subsequent risk of relapse. Also, diagnostic instability is prevalent (e.g., newly arisen depression following remission from an anxiety disorder), markedly increasing the recurrence rates (11)). Moreover, since each new episode of MDD increases the risk of having further episodes (12), efforts needs to be undertaken in order to break this vicious cycle of repeated episodes during adolescence.

According to DSM-5, remission from depression is defined as having no significant symptoms of depression for at least two months. Relapse is then defined as reemergence of clinically significant symptoms of depression within 12 months after remission is being achieved, and if symptoms reemerge after that it is defined as recurrence (13). For anxiety disorders, these boundaries are less defined (14). In practice, relapse and recurrence are difficult to separate, and in ongoing trials on relapse prevention, they are often grouped together (15, 16).

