For exploratory purposes, we will also examine predictors of relapse and predictors for the efficacy of these respective interventions for investigating whom that are most likely to benefit from these different options. In line with recent developments in clinical research, we will address outcome domains relevant from the adolescent perspective, like well-being and self-reported symptom load (37), described below.

SECONDARY OUTCOMES (between trial entry, at 3 months, 6 months, and 12-months):

Repetitive negative thinking - RNT-10 (38) assess transdiagnostic repetitive negative thinking, such as worry and rumination. The questionnaire will be translated into Norwegian by means of a back-translation procedure.

Somatic complaints – SSS8 is an 8-item questionnaire about somatic complaints, freely available and translated into Norwegian (39).

Well-Being - EPOCH Measure of Adolescent Well-Being(40) is a 20-item validated questionnaire that is freely available and will be translated into Norwegian by means of a back-translation procedure.

Health related Quality of Life - EQ-5D-5L + EQ VAS (41, 42) is available in Norwegian and will be used for economic evaluation of the interventions.

Use of health care services – adapted version of the Client Service receipt inventory (CSRI) will assess use of health services, medication use, and school absence.

ASSESSMENTS: Assessments at baseline will serve as predictors of outcome, and include age, gender, parental educational level as proxy for socioeconomical status, in addition to the assessments listed as secondary outcomes. Adolescents are required to fill in questionnaires repeatedly at 3, 6 and 12-month follow up. To maintain fidelity to the trial and prevent fatigue, we have prioritized short, validated scales. All assessments will be conducted within a digital environment (i.e., the research app). In addition to the primary and secondary outcome, at 3-month follow-up, the 8-item Client Satisfaction Questionnaire adapted to Internet-based interventions (CSQ-I (43)) will be administrated to those taking part in one of the two interventional arms.

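### The primary endpoint counts a first depressive episode in an anxiety-only participant as a relapse, so a relapse-prevention claim would include an unknown share of first onsets

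*Protocol*

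**What the plan says.** All references are to the protocol.

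- **Endpoint (Section 1.3, Primary endpoint).** "The primary endpoint will be time until relapse and number of relapses to depression during the 12-months follow-up post-randomization". A PHQ-4 depression score of 3 or more opens the remaining PHQ-A items, and "an algorithm can therefore indicate depressive relapse". The rule is the same for everyone and does not refer to past depression.
- **Who enters (Section 1.3, Participants and Table 1).** The criterion is "Currently in full or partial remission for a minimum of 2 months from a depressive disorder or an anxiety disorder". The CIDI check asks that they "have had a previous episode of depression and/or an anxiety fulfilling the DSM-5 criteria". A past depressive episode is therefore not required.
- **Who is analysed (Section 1.3, Statistical power).** All randomised participants, by intention to treat. Randomisation is stratified by gender only (Section 1.3, Design).
- **What relapse means (Section 1.1).** In a passage attributed to DSM-5: "Relapse is then defined as reemergence of clinically significant symptoms of depression within 12 months after remission is being achieved". The same section gives, as an example of diagnostic instability, "newly arisen depression following remission from an anxiety disorder".
- **What will be concluded (Section 2.1).** Cross-over from anxiety to depression is to be studied as a matter beside relapse. The expected benefit is nevertheless worded as ending repeated depression, and as evidence on interventions against depressive relapse.
- **Related analyses (Section 1.3).** Exploratory work covers "predictors of relapse and predictors for the efficacy of these respective interventions". On the baseline variables: "Assessments at baseline will serve as predictors of outcome, and include age, gender, parental educational level as proxy for socioeconomical status", plus the secondary-outcome scales. Diagnostic history is not named.

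**The concern.** For someone who has never been depressed, a first PHQ-positive result is an onset. The endpoint's name fits participants with past depression and does not fit the others, and Section 2.1 itself keeps the two kinds of event apart. A positive result reported under the present name would be read as fewer relapses to depression, although some of the prevented events may be first onsets. Preventing a return of depression in those who have had it and preventing a first episode in those with past anxiety are different claims. The endpoint as worded does not let a reader tell them apart.

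**Working it through.** **1. Which events carry the label.** Three statements in Section 1.3 settle this: anxiety alone qualifies for entry, every randomised participant is analysed, and one PHQ rule defines the event. A first depressive episode in an anxiety-only participant is therefore a primary event called a relapse. For the count, only that participant's first episode is a first onset, and any later one is a recurrence.

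**2. Inputs.** From the protocol: hazard ratio (HR) 0.6, 15% annual dropout, 1 year, 165 per group, 5% significance level, 80% power. Assumed, because the protocol is silent:
- two-sided test; exponential event and dropout times; HR 0.6 in both history groups;
- anxiety-only share *s* from 10% to 71%. The low end has no source. The high end is only an upper guide from Section 1.3, Risk: 0.05 × 150,000 = 7,500, 0.02 × 150,000 = 3,000, and 7,500/10,500 = 71%. Those are current diagnoses, not the enrolled group, and comorbidity and past depression are ignored;
- hazard in anxiety-only participants *r* = 0.25 to 0.75 times that with past depression.

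**3. The plan's own figure.** Schoenfeld: 4 × (1.960 + 0.842)² / (ln 0.6)² = 120.3, so 121 events per pair of arms. With dropout hazard μ = −ln 0.85 = 0.1625, the 1-year event probability is P(λ) = λ/(λ+μ) × (1 − e^−(λ+μ)). Solving 165 × [P(λ) + P(0.6λ)] = 121 gives λ = 0.637, a 12-month control risk of 47.1%. The 165 per group is thus plausible, but it cannot be reproduced because no control risk is stated. I use 47% (λ = 0.635) as the control risk with past depression.

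**4. Share of first events that are first onsets.** Middle cell, *s* = 50%, *r* = 0.5, so 82.5 of each kind per arm:
- past depression: 82.5 × (0.4375 + 0.2939) = 60.3 events;
- anxiety only: 82.5 × (0.2521 + 0.1605) = 34.0 events;
- share: 34.0/(34.0 + 60.3) = 36.1%.

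| Anxiety-only share | r = 0.25 | r = 0.5 | r = 0.75 |
|---|---|---|---|
| 10% | 3.2% | 5.9% | 8.1% |
| 33% | 12.9% | 21.7% | 28.2% |
| 50% | 23.1% | 36.1% | 44.3% |
| 71% | 42.4% | 58.0% | 66.1% |

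The assumed 47% matters little. For shares of 33-71% the range is 12.0-65.5% at a risk of 30% and 13.7-66.6% at 60%. Hand check of the middle cell in the low-risk limit, *sr*/(*sr* + 1 − *s*): 0.25/0.75 = 33.3%.

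**5. When the label would mislead.** With HR 0.6 in both groups, the pooled HR is also the relapse HR, and nothing is misattributed. Suppose instead that the HR is 1 for relapse and 0.6 for first onset, and approximate the pooled log HR by the event-weighted average, *p* × ln 0.6. The pooled HR is then about 0.98, 0.83 and 0.71 at *p* = 3%, 36% and 66%. Even granting 121 events, power = Φ(|ln HR| × √121/2 − 1.96) is about 17% at 0.83 and 46% at 0.71.

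**6. Validity and gain from adjustment** (simulated two-arm trials, 165 per arm, shares 33-71%, 47% risk). Type I error is 4.3-5.3% unadjusted and 4.4-5.3% adjusted. The unadjusted HR is 0.597-0.615 against a true 0.6. Stratifying the Cox model by history gains 0 to 4.6 power points: about 0 at *r* = 0.75, 0.7-1.5 at 0.5 and 3.5-4.6 at 0.25.

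**7. Precision by history.** The 95% limits lie a factor exp(1.96 × 2/√events) either side of the HR. For shares of 33-71% there are 12.0-68.2 first onsets per pair of arms (factor 3.1 to 1.6) and 35.0-80.9 relapses (1.9 to 1.5). At a 10% share and *r* = 0.25 there are 16.5 × (0.1357 + 0.0839) = 3.6 first onsets (factor 7.9). Power to tell HR 0.6 from HR 1, with standard error √(4/d₁ + 4/d₂), is about 13% with 12.0 and 80.9 events and 26% with 48.0 and 60.3.

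**The case against.** The best defence is that the mix is intended and openly stated. Section 1.1 describes the population as having had depression, anxiety or both, directly before stating the relapse aim. It names anxiety turning into depression as a target, and it links that cross-over to higher recurrence rates. The definition of relapse there is DSM-5 background, not the endpoint definition. Section 2.1 is an impact statement and does commit to studying cross-over. The exploratory predictor analyses could include history, since the baseline list need not be exhaustive. All of this stands, and it reduces the point to one of naming and interpretation. It does not remove it, because the endpoint's name and the conclusions in Section 2.1 are protocol text and do not fit each other.

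Stronger readings that a reader might infer, and that the documents do not support:

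- *The comparison is biased or the error rate inflated.* Arms are randomised and the event rule is uniform, and the simulations show neither.
- *A positive result would really be a first-onset effect.* This needs different effects by history, for which the protocol gives no evidence. Step 5 shows that such a pattern would often fail to reach significance.
- *The trial is underpowered because anxiety-only participants have fewer events.* The protocol states no control risk, so 165 per group may already reflect the mix.
- *The cross-over analysis or history covariate is missing.* Either may sit in the statistical analysis plan, which is not at hand.

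**Conclusion.** The point holds in a limited form and is minor to moderate. The primary event merges relapse with first onset under a name that fits only relapse. First onsets would make up about 3% to 66% of first events. That width comes from two assumed inputs, the anxiety-only share and the relative hazard, and the protocol fixes neither. The intention-to-treat result remains a valid estimate for any depressive episode in the enrolled mix. What it cannot do under the present wording is support a statement about relapse alone, unless the effect is the same whatever the history. The power gain from adjustment is secondary and is not the reason for the change.

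**What to change.** 1. Name the primary event *depressive episode (relapse or first onset)* for both time to event and number of events, and word the conclusions in Section 2.1 to match. For the count, state that only the first episode in an anxiety-only participant is a first onset.
2. Record lifetime depression (yes/no) for every participant from the CIDI pre-assessment and name it among the baseline predictors. Adjust or stratify the primary analyses of both endpoints for it: the Cox model and the analysis of number of events.
3. Report effects by depression history with confidence intervals, as description only. This also serves the cross-over aim in Section 2.1.

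**Cost.** Wording, one baseline variable and one table. Eligibility and the gender stratification stay as they are. The CIDI is already done before randomisation. The protocol does not say that lifetime depression is stored for everyone, so the app must be set up to keep it, including for those who qualify through anxiety. Adjustment has no real downside. The by-history estimates will be imprecise and will seldom separate the two effects, so they should not carry a claim of their own.
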